PROTOCOL CONCEPT SHEET 2 – PROTOCOL

Compound No. E2007

Name of Active Ingredient: Perampanel

Study Protocol Title

An Open-label, Observational, Prospective, Multicenter Study to Evaluate the Long-term Efficacy and Safety of Perampanel as Monotherapy in Subjects Age 4 Years and Older with Focal Onset Seizures

Investigators

[name] (Principal)

Sites

Approximately 10-15 sites in Japan

Study Period and Phase of Development

From April 2021 to December 2024 (from first patient in to last patient out), including a 12-month enrollment period for 30 months of monotherapy treatment or until perampanel is discontinued, whichever comes sooner

Phase 4

Objectives

Primary Objective

The primary objective of the study is to evaluate 24-month seizure freedom in response to perampanel monotherapy in subjects age 4 years and older with focal onset seizures (FOS) (with or without focal-to-bilateral tonic clonic seizures [FBTCS])

Secondary Objectives

1. To evaluate the treatment effectiveness as measured by pragmatic seizure-free rate in response to perampanel monotherapy at 6, 12, 18 and 30 months

2. To evaluate the treatment effectiveness as measured by sustained seizure freedom in response to perampanel monotherapy at 12 and 24 months

3. To evaluate 6, 12, 18, 24 and 30 months retention on perampanel monotherapy in subjects with FOS

4. To evaluate safety and tolerability of perampanel monotherapy in subjects with FOS over the entire study and the specific time points (month 0-3, 4-12 and 13-30)

5. To evaluate the impact of perampanel monotherapy on the subject's quality of life (QOL) from the baseline to the specific time points (month 1, 3, 6, 12, 18, 24, 30)

Exploratory Objectives

1. To explore the effect of perampanel monotherapy on sleep quality using the HARU-1 wearable device

2. To evaluate the treatment adherence of perampanel

3. To explore clinical factors that influence seizure freedom rate in subjects receiving perampanel monotherapy

Study Design

This is an observational, prospective study in subjects with a diagnosis of FOS (with or without FBTCS), for whom the treating physician has made the decision to initiate perampanel as

monotherapy.

Subjects will be identified by sites from the electronic/paper medical and pharmacy records of patients attending their usual epilepsy clinic. The clinical decision to initiate perampanel as monotherapy will already have been made before the subject is identified for the study – ie, the decision to add perampanel is independent of the decision to enroll the subject in the study.

Before any study procedures, signed informed consent/assent form must be first obtained (informed assent [verbal only] will be taken from age 7 until 12 years, and informed assent [verbal + sign] will be taken from age 13 to 19 years. In addition, legal representatives should signed informed consent on behalf of subjects who are less than 20 years). Subjects will then enter into Screening Period for eligibility determination. Demography and medical history (including epilepsy history and baseline seizure frequency based on retrospective collection from 3 months before Day 0 [day of first dose of perampanel]) will be collected. Subjects, age 20 years or older who have provided informed consent and who report a tendency to a poor night's sleep, defined as a subjective sleep onset latency [sSOL] of 30 minutes or more, or subjective wake after sleep onset [sWASO] of 60 minutes at least 3 times a week over the previous month will be participate in the sleep substudy. They will be provided with a HARU-1 wearable device and instructed in its use for recording of baseline sleep parameters.

Subjects who are eligible will then enter the Treatment Period and perampanel monotherapy will be initiated. During the Treatment Period, data will be collected prospectively via 2 types of assessments: on-site and off-site.

- For on-site assessments, site visits and visit frequency during the treatment period are based on clinical practice. When subjects visit the site, concomitant medication use and treatment-emergent adverse events (TEAEs) will be recorded using electronic data capture (EDC) system.
- For off-site assessments, subjects will be provided with an electronic patient report outcome (ePRO) device and instructed in its use for recording seizure diaries, study drug adherence, and QOL (EQ-5D-5L, VAS and PedsQL). The seizure diaries input can be recorded at anytime when a seizure occurs and the presence or absence of a seizure is confirmed once a month via ePRO device reminder. Study drug adherence and QOL assessments will be performed at 1, 3, 6, 12, 18, 24 and 30 months. For subjects less than 18 years old, family members/caregivers should enter on behalf of the subjects. For sleep substudy, subjectswho have received perampanel monotherapy for at least 3 months after treatment initiation and remain stable at target dose of 4-8 mg/day for at least 4 weeks will have post-baseline sleep measurements taken onceusing the HARU-1 wearable device at any time until Months 12. The data on the time that subjects start trying to sleep and the time they get up in the morning will be recorded using the device by pressing the button on the device.

Subjects who discontinue perampanel because of adverse events or other reasons will be followed up approximately 1 month (+ 2 weeks) after last dose for TEAE/serious adverse event (SAE) follow up and subjects will need to completed ePRO assessment at perampanel discontinuation and 1 month (+ 2 weeks) after.

Number of Subjects

Approximately 60 subjects

Inclusion Criteria

1. Male or female, age 4 years or older at the time of informed consent (in the case of minors, consent from a legal representative [eg, one parent] is required)

2. Diagnosed with FOS (with or without FBTCS) according to International League Against Epilepy (ILAE) 2017 classification

3. Newly diagnosed or recurrent epilepsy. For subjects with recurrent epilepsy, they must have relapsed at least 2 years after the end of the last antiepileptic drug (AED) treatment.

4. Subjects for whom the decision to initiate perampanel has been made, according to the judgment of the investigator

Specific criteria for participating in the sleep substudy

5.1 Subjects age 20 years or older who agree to participate in sleep assessments.

5.2 Subjects who self report a tendency to a poor night's sleep defined as a sSOL of 30 minutes or more, or sWASO of 60 minutes, for at least 3 times a week over the previous month

Exclusion Criteria

1. A history of receiving any AED (including AED used as rescue treatment) for more than 2 weeks in total within 2 years before Day 0

2. Previously treated with perampanel at any time

3. A history of hypersensitivity to any of the excipients of perampanel

4. Severe hepatic impairment

5. Subjects who have participated in a study involving administration of an investigational drug/biologics or device within 4 weeks or within approximately 5 half-lives of the investigational drug/biologics, whichever is longer, before screening.

6. Not appropriate for the study according to the judgment of the investigator

Study Treatment

Not applicable, this is an observational study. Perampanel will be administered as per the judgment of the treating clinician.

Duration of Treatment

Subjects will be observed for up to 30 months (2.5 years) after initiation of perampanel monotherapy.

Concomitant Drug/Therapy

Not applicable.

Assessments

Demography data will be collected and recorded during screening period. It will consist of gender, age, hospitalization/outpatient, pregnancy, height, weight, history of drug allergies, comorbidities, complications, concomitant medications. Data from the treatment period will be obtained and recorded using EDC and the ePRO device. Concomitant medication and TEAEs will be recorded using EDC at each subject visit. Seizure diaries, study drug adherence, and QOL assessments will be recorded using an ePRO device provided to each subject.

Efficacy Assessments

1. Retention on perampanel will be assessed by treatment status (ongoing on perampanel or not) at each visit. Reasons for discontinuation will be recorded.

2. Number of seizures will be collected from the ePRO device. Subjects or their family members/ caregivers will be instructed in its use for recording seizure diaries. The seizure diaries input can be recorded at anytime when a seizure occurs and the presence or absence of a seizure is confirmed once a month via ePRO device reminder. This information will be recorded, sent to the data server, and used to calculate the seizure freedom. Seizure frequency data will be collected retrospectively during the 3 months up to the day before Day 0 to ensure adequate data to calculate baseline seizure frequency per 28 days.

Pharmacokinetic Assessments

Not applicable.

Pharmacodynamic, Pharmacogenomic, and Other Biomarker Assessments

Not applicable.

Safety Assessments

Safety assessments will consist of monitoring and recording all TEAEs. Information on TEAEs will be collected by open/general questions to subjects at each visit. Any spontaneously reported TEAEs between visits will also be captured. Exposure to perampanel will be assessed by recording perampanel dose at each visit.

Other Assessments

1. Overall QOL will be assessed using the EQ-5D-5L (with VAS) questionnaires with ePRO device for adult (16 years and older). For children from 12 to less than 16, it can be self-completed on a case-by-case basis. For children less than 12 years of age, it should be completed by parent/proxy.

The EQ-5D is the most widely used multi-attribute utility (MAU) instrument for measuring health-related quality of life in cost-effectiveness analysis. Questionnaires should be self-read and self-completed unless the subject has a physical disability that prevents him or her from doing so, or for children who are unable to do so. In these cases, a caregiver or study coordinator should read and/or record the subject's answers.

2. Psychosocial quality of life will be assessed using the PedsQL-Generic core scale questionnaires (emotional functioning, social functioning, and work/studies functioning domains) with ePRO device for adult (26 years and older), young adult (18-25 years old), adolescent (13-17 years old, children (8-12 years old), and young children (5-7 years old). PedsQL will not be administered for subjects 4 years of age as of date of informed consent.

The PedsQL Measurement Model is a 23-item modular approach for measuring health related quality of life in individuals in all age rangeswith acute and chronic health conditions. It is responsive to clinical changes over time. Questionnaires should be self-read and self-completed unless the subject has a physical disability that prevents him or her from doing so, or is unable to do so (e.g illiterate; pre-school). In these cases, a caregiver or study coordinator should read and/or record the subject's answers using the subject age-specific proxy versions of the PedsQL. For adult (26 years and older) and young adult (18-25 years old) there will be self administered only, and for adolescent (13-17 years old), children (8-12 years old), and young children (5-7 years old), there will be both self administered and proxy administered.

3. Brain wave activity during sleep will be assessed using the HARU-1 device.

HARU-1 is a palm-sized wearable device with a highly accurate patch-type EEG sensor to measure brain wave activities using multi-channel, stretchable, and user safety electrode sheet. The sensor makes continouous brain wave measurement possible for up to 10 hours. The data are sent automatically via bluetooth to the data center. Total sleep time (minutes of sleep from sleep onset until lights on), sleep efficiency (proportion of total sleep time per time spent in bed), sleep latency (estimated minutes from the time that the subjects attempts to sleep until sleep onset), WASO (minutes of wake from the onset of persistent sleep until lights on) and duration of sleep stage will be recorded.

4. Clinical factors to predict efficacy

Data for clinical factors to predict efficacy will be taken and recorded as medical history at the screening period, which are baseline seizure frequency, age at diagnosis, time since diagnosis, etiology (idiopathic, structural), and epileptic focus. Additionally, seizure freedom status at 3 months will also be considered as clinical factors.

5. Study drug adherence

Adherence on perampanel will be input by subjects using the ePRO device.

Bioanalytical Methods

Not applicable.

Statistical Methods

Data will be analyzed according to the Statistical Analysis Plan (SAP) using SAS or other validated statistical software, as necessary. The data will be fully tabulated with summary statistics for continuous variables and frequency and percent for categorical variables. Graphs, using summary values and individual line plots as appropriate, will be used to describe the data.

Study Endpoints

Primary Endpoint

1. Pragmatic seizure free rate at 24 months

Secondary Endpoints

1. The pragmatic seizure-free rate at 6, 12, 18 and 30 months

2. The sustained seizure-free rate at 12 and 24 months

3. Retention rate at 6, 12, 18, 24 and 30 months

4. Incidence of TEAEs over the entire study and the specific time points (month 0-3, 4-12 and 13-30)

5. Change from baseline in EQ-5D-5L and PedsQL to the specific time points (month 1, 3, 6, 12, 18, 24, 30)

Exploratory Endpoints

1. Change from baseline in total sleep time, sleep efficiency, sleep latency, WASO, and duration of sleep stage at the post-baseline measurement (at least 3 months after treatment initiation and remain stable at target dose of 4-8 mg/day for at least 4 weeks) until Months 12

2. Study drug adherence rate at month 1, 3, 6, 12, 18, 24 and 30

3. Clinical factors to predict seizure freedom at 3, 12 and 24 months

Analysis Sets

1. The Safety Analysis Set is the group of subjects who received at least 1 dose of perampanel and had at least 1 postdose safety assessment.

2. The Full Analysis Set (FAS) - All subjects who received at least 1 dose of perampanel will be included in the FAS.

Efficacy Analyses

1. For sustained seizure freedom rate: the number (percentage) of subjects with FOS who achieved seizure-freedom throughout the entire specified time period (numerator) as assessed in the FAS (denominator). Kaplan-Meier will be performed for survival analysis.

2. For pragmatic seizure-free rate: the pragmatic seizure-free rate at 6, 12, 18, 24 and 30 months in the FAS (the number of subjects free of all seizures at 6 months [and for the previous 3 months], and free of all seizures at 12, 18, 24 and 30 months [and for the previous 6 months][numerator], as a proportion of the FAS[denominator]). There will be no imputation for missing data – subjects

with missing data or not ongoing on perampanel at 6, 12, 18, 24 and 30 months will be assumed not to be seizure free.

3. For retention rate: the number (percentage) of subjects remaining on perampanel during the specified time period as assessed in the FAS.

Pharmacokinetic, Pharmacodynamic, Pharmacogenomic, and Other Biomarker Analyses Not applicable.

Pharmacokinetic Analyses

Not applicable.

Pharmacodynamic, Pharmacogenomic, and Other Biomarker Analyses

Not applicable.

Safety Analyses

All safety analyses will be performed based on the Safety Analysis Set. Safety will be assessed over the entire study and also at specific timepoints (month 0-3, 4-12 and 13-30).

The TEAE verbatim descriptions (investigator terms from the case report form [CRF]) will be coded to system organ class (SOC) and preferred terms (PT) using the Medical Dictionary for Regulatory Activities (MedDRA). The number (percentage) of subjects with TEAEs and serious adverse events (SAEs) will be summarized by MedDRA SOC and PT. The incidence of TEAEs will be summarized by severity (mild, moderate, or severe). Categorical variables (age range) will be summarized as number (percentage) of subjects by visit. Exposure to perampanel will be assessed by recording perampanel dose at each visit. Discontinuations because of adverse events will be analysed.

Other Analyses

1. QOL:

- Overall QOL will be reported as the change in EQ-5D-5L score from the baseline at each designated time.
- QOL will be reported as the change in the PedsQL-Generic core scales from the baseline at each designated time. Paired t-test will be performed for significance. To obtain the total scale score, scoring will be done following the PedsQLTM algorithm.
- 2. Total sleep time, sleep efficiency, sleep latency, WASO, and duration of sleep stage
 - The changes from baseline in sleep variables (total sleep time, sleep efficiency, sleep latency, WASO, duration of sleep stage) collected in the HARU-1 device at the post-baseline measurement at any time until Months 12 will be determined. Each variable recorded in the device will be calculated using the data from 1 day or mean of the last 3 days before the visit.
- 3. Clinical Factor to predict efficacy
 - Logistic analysis will be performed. The dependent variable will be seizure free or not seizure free. Baseline seizure frequency, age at diagnosis, time since diagnosis, etiology (idiopathic, structural), and epileptic focus will be assessed individually in univariate analyses; however, all variables will be evaluated using multivariate analyses with forward, backward, or no selection. This analysis is aimed to identify potential predictive clinical factors for achieving seizure freedom or not in subjects with FOS at 3, 12 and 24 months. Additionally, seizure freedom at 12 and 24 months
- 4. Study drug adherence rate

- The number (percentage) of subjects with more than 80%, 50 to 80%, and less than 50% perampanel taken will be summarized. Calculations of adherence are a snapshot of each designated time point (month 1, 3, 6, 12, 18, 24 and 30).

Interim Analyses

Since there is still lack of real world data of perampanel monotherapy, the length of the study, and perampanel LOE approaching soon, we want to make earlier publication. Thus, a total of 2 interim analyses are planned to be conducted. The first interim analyses will be conducted when all subjects have provided 6 months of data and the second one will be conducted when 12 months of data have been provided.

Sample Size Rationale

This study aims to collect data from approximately 60 subjects. No formal sample size calculation has been made, but this sample size is considered appropriate for an observational, open-label study. Assuming that the frequency of perampanel use is about 1.2 cases per month at epilepsy-specialized facilities that are actively prescribing perampanel monotherapy, it is estimated there would be approximately 120 cases annually at 10 facilities. Although this study is an observational study, the target number of subjects was set at 60, assuming that the consent acquisition rate will be 50% because the subjects required a certain degree of information and communications technologies (ICT) literacy. If additional facilities. In addition, it is estimated that about 30% of wearable devices will be implemented, thus it will secure around 20 cases for the analysis.

Study Period Timing	Screening Period Month -1 to Day 0	Treatment Period									
		Day 0	Month 1 ^a	Month 3 ^a	Month 6 ^a	Month 12 ^a	Month 18 ^a	Month 24 ^a	Month 30 ^a /DC	FU after DC ^b	
Dn-site assessments (di	uring site visit	$)^a$	1		1	1		1			
Informed Consent ^c	X										
Demography	Х										
Medical history (including epilepsy history)	Х										
Inclusion/exclusion criteria	X										
Perampanel prescription ^d		X ^d									
Prior/Concomitant medication ^d	X		X^d								
Adverse event ^d			X^d								

1										
Seizure diaries ^e					•	•			•	X
EQ-5D-5L and										
PedsQL ^e		X	X	X	Х	Х	Х	Х	Х	Х
Study drug adherence ^e			Х	Х	X	X	Х	X	X	Х
Sleep assessment	$(X)^{f}$				$(X)^g$					
DC = discontinuation, eP	RO = electr	ronic patient	reported ou	tcome, FU =	follow-up, Q	OL = quality	of life, LPS	= latency to	persistent sle	ep,
TEAE = treatment emerg		-	-		17 1		,	5	1	1 '
a. Each evaluation date is specified based on the date of Day 0, and each evaluation date should be implemented within ± 7 days of the specified date.										
 b. For discontinued cases, follow-up evaluation will be conducted 4 weeks (+ 2 weeks) after last dose for TEAE/SAE follow up. 										
c. Obtain consent by electronic or paper based application. Informed consent/assent must be obtained before any study related procedure.										
d. Site visit schedule du										
e. Subjects will enter data for seizure diaries, QOL, and study drug adherence using the ePRO device. For subjects less than 18 years old, family members/caregivers should enter on behalf of the subjects. The seizure diary input can be recorded at anytime when a seizure occurs, but the presence or absence of a seizure is confirmed once a month via ePRO reminder. For study drug adherence, subject will answer a question to review their adherence in the past one-month period at each designated time points.										
At screening, the wearable device will be provided only for the subjects who have provided consent to sleep assessment and who report a tendency to a poor night's sleep (defined as a subjective sleep onset latency [sSOL] of 30 minutes or more, or subjective wake after sleep onset [sWASO] of 60 minutes), which are self-reported in the medical interview for at least 3 times a week over the previous month. Subject will be asked to take sleep measurements use the device for 1 day or mean of the last 3 days.										
	nly for subjects who have been on perampanel monotherapy for at least 3 months after treatment initiation and remain stable at target dose of 8 mg/day for at least 4 weeks will have post-baseline sleep measurements taken once using the HARU-1 wearable device at any time until

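### Who answers the quality-of-life questionnaires under age 18 is stated inconsistently, so change from baseline may mix proxy and self reports; the PedsQL score is also inconsistently defined

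*Protocol*

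**What the plan says.** Change from baseline in EQ-5D-5L and PedsQL is the fifth secondary endpoint, at months 1, 3, 6, 12, 18, 24 and 30. The Protocol says who responds in three places.

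- **Study Design, off-site assessments.** After listing diaries, adherence, EQ-5D-5L, VAS and PedsQL as ePRO content, it states: "For subjects less than 18 years old, family members/caregivers should enter on behalf of the subjects".
- **Schedule of assessments, footnote e.** The same sentence follows directly on "Subjects will enter data for seizure diaries, QOL, and study drug adherence using the ePRO device", so the under-18 rule covers QOL and not only the seizure diary.
- **Other Assessments, items 1 and 2.** EQ-5D-5L is given as "questionnaires with ePRO device for adult (16 years and older"). Below that age: "For children from 12 to less than 16, it can be self-completed on a case-by-case basis", and "For children less than 12 years of age, it should be completed by parent/proxy". For PedsQL, self-completion is first the default, with proxy versions for those unable to do it. Then, for ages 5 to 17, "there will be both self administered and proxy administered". From 18 PedsQL is by self-report alone.

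On the PedsQL score, Other Assessments item 2 says "Psychosocial quality of life will be assessed using the PedsQL-Generic core scale questionnaires" and names the emotional, social and work/studies domains, while describing a 23-item instrument. Other Analyses item 1 then says "To obtain the total scale score, scoring will be done following the PedsQLTM algorithm". It analyses PedsQL change with a paired t-test and EQ-5D-5L as change from baseline, without naming the respondent.

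**The concern.** A within-subject change means what it should only if the same kind of respondent answered at both times. If a parent answers at baseline and the adolescent answers later, the difference contains a change of rater as well as any change in quality of life, and the two cannot be separated afterwards. With contradictory rules, sites and the ePRO set-up may each follow a different one, and a subject can move from one rule to another during 30 months. The only age that the Protocol ties to the date of consent is the exclusion of 4-year-olds from PedsQL; otherwise it does not say whether a subject keeps the baseline respondent or version on growing older.

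The PedsQL score is a separate matter. A text that assesses psychosocial quality of life through three named domains and then derives a total leaves open which items make up the endpoint.

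**Working it through.** The Protocol gives no figure to reproduce. The check compares the rules by age and then gives an illustration of scale.

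**Rules by age**

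| Age | Study Design and footnote e | EQ-5D-5L, Other Assessments | PedsQL, Other Assessments |
|---|---|---|---|
| 4 | caregiver | proxy | not given (aged 4 at consent) |
| 5–11 | caregiver | proxy | self and proxy |
| 12–15 | caregiver | self or proxy, case by case | self and proxy |
| 16–17 | caregiver | adult, so self | self and proxy |
| 18 and over | self | self | self only |

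- EQ-5D-5L: consistent below 12; in conflict at 12–15 whenever self-completion is chosen; in conflict outright at 16–17.
- PedsQL: in conflict at 5–17, because a self-report is required that the general rule appears to give to the caregiver. Item 2 also disagrees with itself, since the proxy version is first an exception and then routine.

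**Where the respondent can change**

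- Under the general rule, both instruments change respondent at 18.
- Under Other Assessments, EQ-5D-5L can change at 12 (self-completion becomes possible) and at 16 (adult). The case-by-case choice at 12–15 is not fixed over time either.
- Under Other Assessments, PedsQL keeps a self-report series from 5 onward, and only the proxy series stops, at 18.

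**Illustration of scale**

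Inputs: follow-up of 2.5 years (Duration of Treatment). Assumptions: ages uniform from 4 to under 18 (14 years wide; 13 for PedsQL, from 5) and every subject followed for the full 30 months. A subject passes age *b* if aged between *b* − 2.5 and *b* at Day 0.

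- EQ-5D-5L, general rule (18): 2.5/14 = 18%.
- EQ-5D-5L, Other Assessments (12 and 16): (2.5 + 2.5)/14 = 36%.
- Any of 12, 16 and 18: ages 9.5–12 (2.5 years) and 13.5–18 (4.5 years, since the windows for 16 and 18 overlap), so 7/14 = 50%.
- PedsQL, general rule (18): 2.5/13 = 19%.
- PedsQL, Other Assessments: no forced change of respondent in the self series.

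These are shares of minors who pass an age limit. Those already self-completing do not switch, and discontinuation before month 30 lowers the shares. The Protocol gives neither the age distribution nor the number of minors among the approximately 60 subjects, so no count follows.

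**PedsQL score.** Three domains are named, no item is expressly left out, the instrument is called 23-item, and a total is derived. The items per domain and the domains entering the total are not stated. If the same items are used at every visit, within-subject change remains comparable; what is unsettled is which score it is.

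**The case against.** The strongest reply is that the under-18 sentence is a general instruction about who enters data, while Other Assessments gives the specific rules on who answers. A caregiver would then merely key in the child's own responses. That is plausible: Other Assessments itself uses helpers partly to read out questions and record the subject's answers. But the Protocol does not say so, and this reading leaves untouched the two PedsQL proxy rules and the open EQ-5D-5L choice at 12–15. It weakens the conflict without removing it.

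A second reply is that naming the analysed report belongs in the SAP, which is not shown. This stands for the choice of report: its absence from the Protocol is not the defect. It does not stand for collection, because no SAP can recover a self-report that was never obtained or undo a switch of respondent.

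A reader might infer that most paediatric subjects are affected, by counting PedsQL age-band crossings: 2.5/3 = 83% for ages 5–7 and 2.5/5 = 50% for 8–12. Those are changes of questionnaire version. Both reports are required on either side of 8 and of 13, so they are not changes of rater, and there is no age distribution to support the word most. A reader might also infer that only psychosocial items are administered and that the total is therefore mislabelled. The text never says only and excludes no item.

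**Conclusion.** The point holds as an inconsistency in the Protocol that puts a secondary endpoint at risk; it does not show that change scores are in fact mixed. The respondent rules conflict for EQ-5D-5L at 12–17 and for PedsQL at 5–17, and agree for EQ-5D-5L below 12. EQ-5D-5L change may combine proxy and self reports in subjects who pass 12, 16 or 18. PedsQL change may do so at 18, but only if the general caregiver rule is applied until then. The extent is unknown; the illustrative shares rest entirely on the uniform-age and full-follow-up assumptions.

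The mismatch between the named PedsQL domains and the total score also holds, as an unclear definition that does not by itself make changes non-comparable. The point concerns the QOL endpoint only. It should be corrected because the ambiguity acts at data collection and the correction is cheap.

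**What to change.** - **One respondent rule.** Reconcile Study Design, Other Assessments and footnote e into a single rule per instrument and age. Say whether a caregiver is the proxy respondent or only keys in the subject's answers, and whether the PedsQL proxy report at 5–17 is routine or an exception.
- **EQ-5D-5L.** Either keep each subject's Day 0 respondent type throughout, stating that this also applies after 12, 16 or 18, or record the respondent type at each assessment and compute change only between scores of the same type.
- **PedsQL.** At 5–17 keep both required reports, analyse self and proxy change separately, and end the proxy series at 18, where the Protocol ends it. Fixing a single PedsQL respondent at Day 0 would not work, because it would drop one of the two required reports.
- **PedsQL score.** Make Other Assessments and Other Analyses agree on which domains are administered and which score is reported.

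The cost is Protocol wording and a check of the ePRO set-up. The drawbacks are smaller cells once self and proxy are shown separately, and some changes that cannot be computed when the respondent changes.

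### The seizure-freedom and retention rules require only that the subject is still on perampanel, so subjects who add a second AED can be counted in rates meant to describe monotherapy

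*Protocol*

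**What the plan says.** The primary objective is to "evaluate 24-month seizure freedom in response to perampanel monotherapy in subjects age 4 years and older with focal onset seizures". Secondary objective 3 is "To evaluate 6, 12, 18, 24 and 30 months retention on perampanel monotherapy in subjects with FOS". The primary endpoint is named only as "Pragmatic seizure free rate at 24 months"; its content is in Efficacy Analyses, item 2.

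Under that item, the numerator at month 24 is subjects free of all seizures at that time and for the previous 6 months, and the denominator is the FAS (at least one dose of perampanel). Subjects "with missing data or not ongoing on perampanel at 6, 12, 18, 24 and 30 months will be assumed not to be seizure free".

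Retention is defined in Efficacy Analyses, item 3, as "the number (percentage) of subjects remaining on perampanel during the specified time period as assessed in the FAS". Efficacy Assessments, item 1, gives the measurement: "Retention on perampanel will be assessed by treatment status (ongoing on perampanel or not) at each visit".

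Study Period describes follow-up as "30 months of monotherapy treatment or until perampanel is discontinued, whichever comes sooner". Treatment is left to the treating clinician, and concomitant medication is recorded in the EDC at each visit. No section says whether adding a second AED ends monotherapy, counts as discontinuation or makes the subject a failure.

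**The concern.** The objectives name a regimen, perampanel alone. The counting rules name a drug, perampanel with or without anything else. The two agree only for subjects who never add another AED.

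The pragmatic definition is the more exposed of the two seizure-freedom measures because it looks back only 6 months. Seizures in the first 18 months do not count against the subject at month 24, so a failure of monotherapy followed by successful combination treatment fits the definition of success. Retention is more exposed still, because it carries no seizure condition.

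The Interim Analyses section justifies early publication by the shortage of real-world data on perampanel monotherapy. The 6- and 12-month interim results and the 24-month primary result would be read as monotherapy results. The logistic models for clinical predictors use seizure-free status as the dependent variable and could inherit the same misclassification.

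**Working it through.** **Inputs.** The only planned figure needed is the number of subjects, approximately 60 (Number of Subjects; Sample Size Rationale). Its last step reproduces: 120 cases × 0.50 consent = 60. The protocol gives no expected seizure-free rate, retention rate or add-on rate, so it has no figure of its own to reproduce on this point.

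**Objective and rule side by side.**

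| Quantity | Objective | Counting rule | Added AED counts as failure? |
|---|---|---|---|
| Pragmatic seizure-free rate, 24 months | On perampanel monotherapy | No seizures in the 6-month window, no missing data, ongoing on perampanel | No |
| Sustained seizure-free rate, 12 and 24 months | On perampanel monotherapy | No seizures through the whole period | No |
| Retention, 6 to 30 months | On perampanel monotherapy | Remaining on perampanel | No |

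**One subject traced.** Seizures on monotherapy in year one; second AED added; perampanel continued; no seizures from month 18 to month 24; diary complete.
- Pragmatic rate at 24 months: success.
- Retention at 24 months: retained.
- Sustained rate at 24 months: failure, because of the year-one seizures.

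Under a monotherapy rule the same subject fails all three.

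**Direction.** Anyone who succeeds under a monotherapy rule also succeeds under the rule as written, since the first adds a condition to the second. With the same FAS denominator, the reported rate is therefore equal to or above the monotherapy rate and never below it.

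**Size per subject.** 1/60 = 1.7 percentage points.

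**Size under assumptions.** Let *a* be the share of the FAS who have added an AED while staying on perampanel, and *s* the share of those who are seizure free in the window. Excess in the primary rate = *a* × *s*; excess in retention = *a*. Neither *a* nor *s* is in the protocol.

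| *a* | *s* | Primary excess | Subjects of 60 | Retention excess |
|---|---|---|---|---|
| 0.10 | 0.30 | 0.10 × 0.30 = 3.0 points | 1.8 | 10 points |
| 0.15 | 0.50 | 0.15 × 0.50 = 7.5 points | 4.5 | 15 points |
| 0.25 | 0.50 | 0.25 × 0.50 = 12.5 points | 7.5 | 25 points |

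A wider range, *a* from 0.05 to 0.30 and *s* from 0.25 to 0.75, gives 0.05 × 0.25 = 1.25 points up to 0.30 × 0.75 = 22.5 points for the primary rate, and 5 to 30 points for retention.

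**Scale.** The 95% half-width at 60 subjects is 1.96 × √(p(1−p)/60): 12.4 points at p = 0.40 and 12.7 points at p = 0.50. At the low end of the main range the excess is well inside sampling error; at the high end it is about equal to the half-width.

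**The case against.** The best counter-reading is that perampanel in the analysis rules is shorthand for the regimen under study. Study Period speaks of monotherapy treatment, the Treatment Period begins with starting perampanel monotherapy, and Duration of Treatment counts from that start. This does not close the gap. The stop named in Study Period is discontinuation of perampanel, and follow-up after discontinuation is timed from the last dose, so leaving monotherapy is not a stop. Where the authors wanted an on-treatment monotherapy condition, in the sleep substudy, they wrote one.

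A second objection is that the SAP, which was not available for this review, may settle the matter. It may, but the protocol already states the failure criterion and the retention numerator. An SAP requiring monotherapy would depart from that wording.

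Three further objections stand and limit the point.
- Being on perampanel is necessary for primary success but not sufficient: the subject must also have no seizures in the window and no missing data. Only for retention is being on perampanel enough.
- Sustained seizure freedom partly protects the reader, since a subject who adds an AED because of a seizure within the period already fails it. A subject who adds one for another reason does not.
- The study is descriptive, with no formal sample size calculation, and concomitant medication is recorded, so a monotherapy rate could still be derived later.

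A reader might also infer from inclusion criterion 4, "Subjects for whom the decision to initiate perampanel has been made, according to the judgment of the investigator", that subjects can enter without a monotherapy decision. The document does not support this: Study Design limits the population to subjects for whom monotherapy was decided. Exclusion criterion 1 concerns AED exposure before Day 0 and has no bearing on the month 18-24 window. The entry of not applicable under Concomitant Drug/Therapy fits an observational template and is not a counting rule.

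**Conclusion.** The point holds. As written, the primary and retention rules can count a subject who has left monotherapy as a monotherapy success, and the error runs in one direction only. This is a rule that does not match its objective, not a detail left for later.

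The size is not known. It is 1.7 points per affected subject at 60 subjects. Assuming 10-25% add an AED while staying on perampanel and 30-50% of those are seizure free in the window, the primary rate is 3 to 12.5 points too high and retention up to 10-25 points too high. Those shares are assumptions with no source in the protocol.

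A reader might go further and conclude that the results will not be monotherapy results. The document does not support that: if no subject adds an AED and stays on perampanel, the two rules give the same rates. What can be said is that the rule does not ensure monotherapy results.

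**What to change.** In the pragmatic and sustained seizure-free rules, count a subject as not seizure free from the point at which perampanel is discontinued or another AED is added as ongoing treatment. In the retention numerator, count the same subject as not retained on monotherapy from that point. Derive the event from the concomitant medication records already in the EDC. State an analysis convention for how short rescue use is classified, so that ongoing treatment has one meaning across endpoints. Report the rates for still on perampanel, with or without another AED, as supportive. Make the change before the first interim analysis, so that the 6-month, 12-month and 24-month rates share one definition.

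The cost is a few sentences in the protocol and matching text in the SAP. No new data collection is needed, provided the concomitant medication records carry start and stop dates, which the protocol does not spell out and which should be confirmed. The downside is that the reported rates may be somewhat less favourable.
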